2 INTRODUCTION

Tusamitamab ravtansine (SAR408701) is an antibody-drug conjugate (ADC) combining hu769_4D4 (SAR408377), a humanized antibody that recognizes selectively the A3-B3 extracellular domain of CEACAM5, a tumor-associated carcinoembryonic antigen, with the potent cytotoxic maytansinoid derivative, DM4, that inhibits microtubule assembly. Tusamitamab ravtansine is expected to selectively deliver DM4 to cancer cells expressing the CEACAM5 antigen, such as colon, stomach and its signet-ring cell subtype as well as non-squamous NSCLC.

Carcinoembryonic antigen-related cell adhesion molecule 5 (CEACAM5) was first described in 1965 as a tumor-associated antigen in human colon cancer tissue extracts (3). High levels of CEACAM5 expression have since been observed in several epithelial tumors while in normal adult tissue, its expression is limited to few tissues (4, 5). Immunostaining of CEACAM5 in a large panel of human tumor tissue microarray samples has shown the highest prevalence of cell surface CEACAM5 expression in adenocarcinoma of the colon, the stomach and its subtype signet ring cell as well as in non-squamous NSCLC.

2.1 STUDY RATIONALE

In the FIH study TED13751, a cohort of participants with NSQ NSCLC tumors that were CEACAM5-positive (at least 50% of the tumor cell population with membrane immunohistochemical intensity $\geq 2+$) was treated with tusamitamab ravtansine at the recommended dose of 100 mg/m² every 2 weeks. Participants were heavily pretreated before enrollment, with a median of 3 prior treatments (1 to 10 lines) for advanced disease, including antitubulin agents (60.9%) and anti-PD1/PD-L1 (70.3%; 1). Tusamitamab ravtansine showed encouraging antitumor activity in the 64 participants treated in this study, with a response rate of 20.3% (95% CI: 12.27% to 31.71%); 28 participants (43.8%) had SD.

Tusamitamab ravtansine is being developed as a treatment for NSQ NSCLC. The randomized Phase 3 study EFC15858 is currently ongoing to evaluate the efficacy and the safety of tusamitamab ravtansine versus docetaxel in participants previously treated for metastatic NSQ NSCLC who have CEACAM5-positive tumors. The use of combination therapy with tusamitamab ravtansine is also currently being studied in 2 Phase 2 trials in participants with NSQ NSCLC: in second or third-line settings (study ACT16525; tusamitamab ravtansine in combination with ramucirumab in participants with CEACAM5-positive tumors previously treated with platinum-based chemotherapy and an immune checkpoint inhibitor), and in a first-line setting (study ACT16146; tusamitamab ravtansine in combination with pembrolizumab, with or without platinum-based therapy, as first-line treatment in participants with CEACAM5-positive and PD-L1-positive tumors).

Other tumor types also express CEACAM5 in tumor cells known to be sensitive to antitubulin agents such as taxanes (eg, paclitaxel, docetaxel). In the “basket” trial, study ACT16432, the efficacy of tusamitamab ravtansine is being evaluated in metastatic breast cancer (10% prevalence of high expression, defined as $\geq 2+$ in intensity involving at least 50% of the tumor cells) and pancreas (15% prevalence of high expression). The prevalence of high CEACAM expression in gastric cancer is 30%.

In the dose escalation phase of FIH study TED13751 evaluating tusamitamab ravtansine monotherapy, 1 PR was observed in 1 participant with GC. In the GC expansion cohort of this FIH study, a total of 16 participants received tusamitamab ravtansine as monotherapy at 100 mg/m². No objective response was reported for participants in the GC expansion cohort; SD was reported for 37.5% of heavily pretreated (median of 3 prior treatments) participants; 81.3% of participants had prior taxane therapy. In the “loading dose” escalation cohort, 2 participants with GC were treated at the recommended dose (170 mg/m² then 100 mg/m² Q2W); a single participant with GC had nonconfirmed PR (overdosed, having received twice the loading dose), and the other participant achieved SD.

Ramucirumab, an antibody antagonist of vascular endothelial growth factor receptor 2 (VEGFR2), was approved by the US Food and Drug Administration (FDA) as monotherapy for second-line gastric cancer in April 2014, based on the results from the Phase 3 REGARD study (6). The REGARD study compared ramucirumab monotherapy (8 mg/kg IV infusion on Days 1 and 15 every 4 weeks) to best supportive care (BSC) in subjects refractory to previous fluoropyrimidine treatment (with or without platinum). Ramucirumab significantly improved OS (5.2 months compared to 3.8 months with BSC, hazard ratio [HR]=0.776, p=0.047) and PFS (2.1 months as compared to 1.3 months with BSC, HR 0.483, p <0.0001).

Ramucirumab (anti-VEGFR2) combined with the antitubulin agent paclitaxel leads to improved efficacy as compared to paclitaxel single agent as second-line therapy for the treatment of GC. The combination of ramucirumab plus paclitaxel was approved for second-line treatment of GC by the US FDA in November 2014, based on results from the Phase 3 RAINBOW study (2). This study evaluated paclitaxel (80 mg/m² IV on Days 1, 8, and 15 of a 28 day cycle) with or without ramucirumab (8 mg/kg IV infusion on Days 1 and 15 of a 28 day cycle) in subjects with metastatic gastric cancer refractory or progressive after first-line platinum and fluoropyrimidine therapy. Median OS was significantly improved for the combination (9.6 months) compared to paclitaxel alone (7.4 months), with a HR 0.807 (p=0.017). Median PFS was 4.4 months with the combination and 2.9 months with monotherapy, with a HR of 0.635 (p <0.0001) favoring the combination. Adverse events of Grade ≥3 occurring in more than 5% of participants were more frequent with combination treatment as compared to paclitaxel alone; incidences appeared to be elevated with the combination as compared to paclitaxel monotherapy for neutropenia (41% compared to 19%), leukopenia (17% compared to 7%), hypertension (14% compared to 2%), fatigue (12% compared to 5%), anemia (9% compared to 10%), and abdominal pain (6% compared to 3%).

Synergy of the activity of tusamitamab ravtansine (containing the cytotoxic antitubulin agent DM4) in combination with ramucirumab may lead to improved efficacy in the treatment of GC patients with a high unmet need; furthermore, this combination may have a better safety profile as compared to the combination of paclitaxel with ramucirumab. Nonclinical evaluations of the combination of tusamitamab ravtansine with a VEGFR2 antagonist were conducted in mice with GC PDX to evaluate substitution of paclitaxel with tusamitamab ravtansine in combination with ramucirumab. The results of these evaluations support clinical investigation of tusamitamab ravtansine in combination with ramucirumab: more extensive and sustained regression observed in evaluations of tusamitamab ravtansine in combination with the VEGFR2 antagonist as compared with paclitaxel in combination with anti-VEGF2 agent in GC PDX. Additionally, the observed safety profile for the tusamitamab ravtansine and anti-VEGFR2 combination in PDX

mice compared favorably to that observed for the taxol and anti-VEGFR2 combination. Replacing paclitaxel with tusamitamab ravtansine in combination treatment with ramucirumab may improve efficacy and optimize DOR, as well as safety in participants with CEACAM5-positive, antitubulin-agent-sensitive GC, who represent a patient population with a high unmet need.

2.2 BACKGROUND

Gastric cancer is the fifth most common cancer worldwide (7, 8), with 1 089 103 new cases diagnosed in 2020 (9). It is the third most common cause of cancer death, and incidence varies geographically, with approximately half of all cases occurring in east Asia (10). In the United States, an estimated 22 280 cases of gastric cancer were diagnosed and 11 430 participants died from this disease in 2006 (11). Although treatment for participants with unresectable or metastatic disease remains palliative, chemotherapy improves survival and quality of life when compared to BSC. Currently, platinum-based and fluoropyrimidine-based combinations are accepted worldwide as established first-line drug regimens (12). Trastuzumab is a HER2-targeted humanized monoclonal antibody that, in combination with chemotherapy, has also been approved as a first-line treatment for participants with HER2-positive advanced gastric cancer. Ramucirumab (anti-VEGFR2 agent) combined with paclitaxel is a standard-of-care option for second-line treatment.

2.3 BENEFIT/RISK ASSESSMENT

Detailed information regarding known risks and precautions for patients receiving ramucirumab may be found in the Cyramza[®] prescribing information.

2.3.1 Risk assessment

Risk assessment for tusamitamab ravtansine

Based on available safety data, the main identified risk to participants is corneal toxicity presenting as microcystic keratopathy, which is reversible and manageable with dose delay and dose reduction in some participants. Peripheral neuropathy is an identified risk in participants previously exposed to neurotoxic drugs.

Among the 16 participants in the GC cohort treated in FIH study TED13751, the most common TEAEs (reported in >10% of participants) were Asthenia (37.5%), Decreased appetite (31.3%), Fatigue (25%), Dyspnea, Nausea, Abdominal pain, Back pain, Dyspepsia, Disease progression (each in 18.8%), Anemia, Dizziness, Dry eye, Constipation, Vomiting, Ascites, and Edema peripheral (each in 12.5%).

In the loading-dose escalation phase from the FIH study, among the 28 participants treated, the most common TEAEs were: Nausea and Asthenia (each in 21.4%), Keratopathy and Abdominal pain (each in 17.9%), Peripheral sensory neuropathy, Keratitis, Dry eye, Dyspnea, and Diarrhea (each in 14.3%), and Cough, Decreased appetite, and Fatigue (each in 10.7%).

Among the 13 participants treated at the dose of 170 mg/m² at Cycle 1 followed by 100 mg/m² for subsequent cycles Q2W, preferred terms reported as TEAEs (all grades) for at least 2 participants were: Keratopathy, Keratitis, Asthenia, and Nausea (each reported for 4 participants); Decreased appetite, Peripheral sensory neuropathy, Gastroesophageal reflux disease, Proctalgia, Accidental overdose, and Dry eye (each reported for 2 participants). Grade 3 keratopathy was reported for 2 participants. No Grade 4 event was reported. Overall, the safety profile was consistent with what is reported in the main escalation phase of the study; refer to the Investigator’s Brochure for SAR408701 for details of safety data for study TED13751.

Other potential risks were observed in a limited number of patients, and clinical pictures were consistent with a presentation in patients with underlying relevant risk factors. These potential risks include Colitis ([including hemorrhagic], mainly in participants with a known history of colitis or gastrointestinal tract conditions), Cardiotoxicity (myocardial or conduction abnormalities), Hematologic cytopenias, and Hepatotoxicity, as well as Systemic acute hypersensitivity reactions (including anaphylaxis; 1). More detailed information about the known and expected benefits and risks and reasonably expected adverse events (AEs) of tusamitamab ravtansine may be found in the Investigator’s Brochure.

Potential risks for tusamitamab ravtansine and mitigation strategies to be employed in the study are summarized in [Table 2](#).

Table 2 - Risk assessment for tusamitamab ravtansine

Potential risk of clinical significance	Summary of data/rationale for risk	Mitigation strategy
Study interventions: tusamitamab ravtansine		
Microcystic keratopathy	
Nonclinical: Mitotic arrest/single cell necrosis in the cornea of the eye in mice and monkeys. In addition, brown discoloration of the cornea associated, microscopically, with minimal dark pigmentation in cornea epithelial cells in monkeys. Findings considered related to the cytotoxic properties of DM4.
 
Clinical: Main DLT in the dose escalation part of study TED13751. In study TED13751 pooled data: among the 160 patients treated at a dose level of 100 mg/m² Q2W, 51 patients (31.9%) had a corneal TEAE; of these, 13 patients (8.1%) had events ≥ Grade 3. In study TCD15054, of the 6 patients treated at a dose level of 100 mg/m² Q2W, 3 patients (50%) reported a corneal TEAE.
	
Careful collection of medical history and physical examination.
 
Assessment of ocular/visual symptoms at each visit before IMP administration.
 
Specific ocular tests at screening, whenever clinically indicated and at EOT.
 
Wearing of contact lenses is forbidden.
 
Preventive instillation of artificial tears or hyaluronic ophthalmic gel drops.
 
Curative action: dose delay and reduction; artificial tears, corticosteroid eye drops and symptomatic treatment; ophthalmologist follow-up.

Peripheral neuropathy	
Nonclinical: Nerve fiber degeneration in the peripheral nervous system and spinal cord in mice and monkeys. Effects attributed to the tubulin binding properties of DM4 and inhibition of microtubule assembly.
 
Clinical: In study TED13751 at dose level of 100 mg/m² Q2W, 43 patients (26.9%) had at least 1 peripheral neuropathy TEAE. In study TCD15054, 1 patient (16.7%) had peripheral sensory neuropathy.
	
Close surveillance of any signs and symptoms of peripheral neuropathies.
 
This AE is managed by dose delay/reduction as well as treatment discontinuation in case of Grade 3-4.

Potential risk of clinical significance	Summary of data/rationale for risk	Mitigation strategy
Colitis (including hemorrhagic) in patients with a known history of colitis or gastrointestinal tract conditions	
Preclinical: mitotic arrest/single cell necrosis observed in the GI tract (tongue, esophagus, stomach, duodenum, jejunum, ileum, cecum, colon and/or rectum). Therefore, degeneration and villous atrophy was noted in the intestinal mucosa as well as mucosal erosions and/or ulcers. Findings related to the cytotoxic properties of DM4.
 
Clinical: no cases observed in study TCD15054, and very limited occurrence in study TED13751:
 
 • 1 patient developed Grade 3 colitis (pooled data among the 160 patients treated at 100 mg/m² Q2W). • 2 additional patients with colitis in the main dose escalation phase at 120 mg/m² and 150 mg/m² dose levels. 	
Exclusion criterion (see Section 5.2).
 
Close surveillance of any diarrhea event and further investigation when clinically indicated.

Hematologic cytopenias	
Nonclinical: Following a single or a weekly IV administration for 5 weeks of tusamitamab ravtansine in mice and/or cynomolgus monkeys, transient decreases in RBC and WBC, decreases/increases in reticulocytes and decreases/increases in platelets. In addition, mitotic arrest/single cell necrosis associated with a decreased cellularity in the bone marrow and lymphoid tissues. Findings considered related to the cytotoxic properties of DM4.
 
Clinical: no cases observed in study TCD15054, and very limited occurrence in study TED13751:
 
 • Laboratory data showed anemia Grade 3 in 8 patients (5.1%), platelet count decreased Grade 3 in 1 patient (0.6%), and Grade 4 in 3 patients (1.9%). 	
Exclusion criterion (see Section 5.2).
 
Close surveillance of any signs and symptoms.
 
Routine blood hematology workup, Hemoglobin, hematocrit, WBC with differential, platelet counts. These tests will be performed before IMP administration at each visit. During the first 2 cycles, they will be performed on weekly basis. If Grade 4 neutropenia, assess ANC every 2 to 3 days until ANC $\geq 0.5 \times 10^9/L$.

Cardiotoxicity (myocardial or conduction abnormalities)	
Nonclinical: Occasional minimal or mild degeneration/necrosis in the heart observed in single- and repeat-dose weekly for 5 weeks toxicity studies in monkeys. In the weekly for 5 weeks toxicity study in monkeys, compound-related effects on ECG parameters observed in some monkeys at the top dose (7 mg/kg/adm) using an external telemetric methodology (reversible marked increase in HR and non-reversible long-lasting episodes of bundle branch block suggesting an alteration in ventricular conduction which could nevertheless not be evidenced quantitatively (no widening of QRS complex duration) in the present experimental conditions.
 
Clinical:
 
 • In study TCD15054 no case was observed • In study TED13751 pooled data, the following AEs were each reported for 1 patient: angina pectoris, atrioventricular block first degree, bundle branch block right, Electrocardiogram QT prolonged. 	
Exclusion criterion (see Section 5.2).
 
Cardiovascular examination.
 
Monitoring of potential cardiac conduction defects by regular ECG.

Potential risk of clinical significance	Summary of data/rationale for risk	Mitigation strategy
Hepatotoxicity	
Nonclinical: Following a single IV administration of tusamitamab ravtansine in mice and/or cynomolgus monkeys, increased aspartate AST, alanine ALT, ALP and/or GLDH have been noted. In addition, this was associated with mitotic arrest/single cell necrosis observed in the liver. These findings are considered related to the cytotoxic properties of DM4.
 
Clinical:
 
 In study TED13751 pooled data under hepatobiliary disorders SOC, 3 patients (1.9%) had hepatocellular injury events including 1 patient (1.3%) with Grade 4, 1 patient with a hepatic function abnormal event, and 1 patient with hypertransaminasaemia. Clinical laboratory data showed ALT increased Grade 3 in 2 patients (1.3%) and Grade 4 in 2 patients (1.3%); AST increased Grade 3 in 6 patients (3.8%) and Grade 4 in 3 patients (1.9%); ALP increased Grade 3 in 14 patients (8.9%; none with Grade 4), and blood bilirubin increased Grade 3 in 6 patients (3.8%; none with Grade 4). In study TCD15054, AST increased was reported for 1 patient (16.7%). No "Hy's law" cases have been observed. 	
Exclusion criterion (see Section 5.2).
 
Close surveillance of any signs and symptoms of hepatotoxicities.
 
Liver function tests will be performed before IMP administration at each visit. During the first 2 cycles, they will be performed on a weekly basis.
 
In case of Grade ≥ 3 liver function abnormal tests, additional tests will be repeated every 2-3 days until recovery to baseline value.

Systemic acute hypersensitivity reactions (including anaphylaxis)	
Nonclinical: Not observed.
 
Clinical:
 
 in study TED13751 pooled data, 2 patients, including 1 patient (0.6%) with Grade 3 hypersensitivity and 1 patient had Grade 1 infusion-related reaction. in study TCD15054, 1 patient (33.3%) developed rash. 	
Premedication with histamine H1 antagonist.
 
If a patient has previously experienced an infusion-related reaction in a previous tusamitamab ravtansine administration, premedication will also include dexamethasone 10 mg IV for future infusions.
 
Target infusion time is 1.5 h. In case of an IRR, the flow rate can be decreased; minimum authorized flow rate is 33 mL/h. Recommended curative action: In case of infusion reaction \geq Grade 2, tusamitamab ravtansine administration will be interrupted. The infusion may be resumed at half of the previous infusion rate after the recovery.

Abbreviations: ALT = alanine aminotransferase; ALP = alkaline phosphatase; ANC = absolute neutrophil count; AST = aspartate aminotransferase; DLT = dose-limiting toxicity; ECG = electrocardiogram; EOT = end of treatment; GLDH = glutamate dehydrogenase; IMP = investigational medicinal product; IRR = infusion-related reaction; IV = intravenous; SOC = system organ class; TEAE = treatment-emergent adverse event; Q2W = every 2 weeks; RBC = red blood cell count; WBC = white blood cell count.

Ramucirumab

Ramucirumab, a human IgG1 monoclonal antibody that inhibits VEGFR-2, in combination with paclitaxel, has been approved in for the treatment of patients with gastric cancer. Potential and identified risks associated with ramucirumab in gastric cancer are summarized here; more detailed information about the known and expected benefits and risks and reasonably expected adverse effects of ramucirumab and recommended mitigation measures may be found in the US Package Insert or Summary of Product Characteristics/SmPC for Cyramza®.

The most common serious adverse drug reactions (ADRs) associated with ramucirumab were: anemia (3.8%) and intestinal obstruction (2.1%).

The most common ADRs (all grades) observed in ramucirumab-treated patients at a rate of $\geq 10\%$ and $\geq 2\%$ higher than placebo were hypertension and diarrhea (6).

In Ramucirumab Administered in Combination with Paclitaxel (RAINBOW), the most common serious adverse reactions in patients who received ramucirumab with paclitaxel were neutropenia (3.7%) and febrile neutropenia (2.4%; 2). The most common adverse reactions (all grades) observed in patients who received ramucirumab with paclitaxel at a rate of $\geq 30\%$ and $\geq 2\%$ higher than placebo with paclitaxel were fatigue/asthenia, neutropenia, diarrhea, and epistaxis.

Safety profile for the combination

No overlap in the safety profiles for tusamitamab ravtansine and ramucirumab is anticipated. Given the risks of adverse effects including neutropenia, anemia, and infection associated with paclitaxel, the combination of tusamitamab ravtansine with ramucirumab may represent a treatment regimen with an improved safety profile as compared to the approved combination of paclitaxel and ramucirumab.

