Investigational medicinal products:

Ramucirumab: Ramucirumab should be administered prior to tusamitamab ravtansine infusion. Using a controlled infusion pump, ramucirumab will be administered by IV infusion over 1 hour on Day 1 of each cycle. If the first infusion is tolerated, all subsequent ramucirumab infusions may be administered over 30 minutes. In case of IRR, Grade 1 or 2, the infusion rate of ramucirumab will be reduced by 50%.

Tusamitamab ravtansine: Infusion of tusamitamab ravtansine should be initiated after the end of ramucirumab infusion. As IRRs may occur during or following ramucirumab administration, a 1 hour observation period following the ramucirumab infusion is mandatory prior the initiation of tusamitamab ravtansine administration for the first 2 infusions. If the patient shows no evidence of an IRR with the first 2 infusions of ramucirumab, no observation period is required for subsequent infusions. In the event an IRR occurs thereafter, the 1 hour observation should be reinstated.

Using a controlled infusion pump, tusamitamab ravtansine will be administered by IV infusion over 1 hour 30 minutes. For a participant with a BSA >2.2 m², the calculated dose of tusamitamab ravtansine will be based on a BSA of 2.2 m². After the first administration of tusamitamab ravtansine, participants should be observed for acute reactions on site for up to 4 hours depending on any sign of IRR. In case of a Grade 1-2 IRR, tusamitamab ravtansine must be interrupted and may be resumed only after patient recovery, at half of the previous infusion rate, with a minimum authorized flow rate at 33 mL/h. Detailed instructions for dilution and administration of the IMP is provided in Pharmacy Manual.

Noninvestigational medicinal products:

Premedication:

Both tusamitamab ravtansine and ramucirumab have potential risk of IRR; thus, premedication with an IV histamine-1 receptor antagonist (diphenhydramine 50 mg IV or equivalent; eg, cetirizine, promethazine, dexchlorpheniramine, according to local approval and availability) will be given approximately at least 15 minutes before ramucirumab administration. If a participant previously experienced an IRR following a dose of ramucirumab or tusamitamab

ravtansine, premedication will also include corticosteroids equivalent to 10 mg IV dexamethasone, and acetaminophen/paracetamol for future infusions. All drugs used as premedication will be entered on the concomitant premedication page.

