Any patient who has had 1 tusamitamab ravtansine dose reduction or 2 ramucirumab dose reductions and who experiences an event that would cause an additional dose reduction must be discontinued from tusamitamab ravtansine/ramucirumab.

If 1 of the 2 drugs (tusamitamab ravtansine or ramucirumab) is prematurely permanently discontinued, the other drug can be continued until disease progression.

Retreatment of a patient requiring a dose delay of more than 1 month will need to be justified by an individual case risk-benefit assessment.

6.5.1 Retreatment criteria: Part 1 and Part 2

All participants entered into the study will be treated at Day 1. A participant may receive additional study interventions if he/she meets retreatment criteria as determined by the Investigator and agrees to be retreated.

At Day 1, the participant must meet all of the following criteria to be eligible for retreatment:

- Neutrophil count $\geq 1.5 \times 10^9/L$.
- Platelets $\geq 100 \times 10^9/L$.
- Total bilirubin $\leq 1.5 \times ULN$.
- AST, ALT $\leq 2.5 \times ULN$ or $\leq 5 \times ULN$ in case of documented liver metastasis.
- No IMP-related toxicity Grade >1 (except for alopecia) or baseline severity.

- Urine protein:
 - <2+ on dipstick or urinalysis for C1D1
 - ≤2+ on dipstick or urinalysis for subsequent infusions
- OR
- <2 g on 24 hour urine collection.
- Hypertension is controlled. Every attempt should be made to control blood pressure (<150 mmHg systolic and <90 mmHg diastolic).
 - Wound healing: any wound is fully healed.

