8.2.7 Guidelines for management of adverse events

Management of AEs related to tusamitamab ravtansine and ramucirumab is summarized in Appendix 6 ([Section 10.6](#)); for specific AE related to ramucirumab intake, please refer to the current prescribing information leaflet; the most relevant reported events are summarized in this section as reminder.

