Infusion-related reactions	Grade 1-2 Mild-moderate Eg, Grade ≤ 2 nausea, headache, tachycardia, hypotension, rash, shortness of breath.	Interrupt ramucirumab infusion and start appropriate treatment. Reduce infusion rate by 50%	Interrupt tusamitamab ravtansine infusion. Tusamitamab ravtansine may be resumed only after patient recovery, at half the previous infusion rate ^a .	Give diphenhydramine 50 mg IV and/or dexamethasone 10 mg IV. ramucirumab label should be followed Dexamethasone can be added as premedication for upcoming cycles for tusamitamab ravtansine
	Grade 3-4 Severe Eg, symptomatic bronchospasm, urticaria lesions covering >30% BSA, hypotension, angioedema.	Interrupt ramucirumab infusion and definitively discontinue ramucirumab	Interrupt tusamitamab ravtansine infusion and definitively discontinue tusamitamab ravtansine and consider infusion delay.	Give diphenhydramine 50 mg IV and/or dexamethasone 10 mg IV and/or epinephrine and any required treatment per investigator judgement.
Ocular toxicity: Keratopathy/keratitis ^b associated with tusamitamab ravtansine	Grade 1 - Asymptomatic Corneal lesions only observed on routine ocular examination and not requiring topical treatment.	Administer ramucirumab at same dose, and same day as tusamitamab ravtansine	Next infusion of tusamitamab ravtansine at the same dose, with or without cycle delay, depending on the recommendation from the ophthalmologist (nature and extent of the lesion).	Standard ocular examination is planned as recommended by the ophthalmologist.

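### Protocol Table 2 allows tusamitamab ravtansine to be resumed after an infusion reaction of Grade 2 or higher with no upper grade, which contradicts the permanent stop at Grade 3-4 in Appendix 6

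*Protocol*

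**What the plan says.** Four places in the protocol deal with an infusion-related reaction (IRR) to tusamitamab ravtansine.

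- **Table 2, Section 2.3.1**, row on systemic acute hypersensitivity including anaphylaxis. For any IRR: "In case of an IRR, the flow rate can be decreased; minimum authorized flow rate is 33 mL/h". For a reaction at or above the stated grade: "Grade 2, tusamitamab ravtansine administration will be interrupted. The infusion may be resumed at half of the previous infusion rate after the recovery".
- **Section 6.1**, the administration instructions: "In case of a Grade 1-2 IRR, tusamitamab ravtansine must be interrupted and may be resumed only after patient recovery", at half the earlier rate and with the same 33 mL/h floor. It gives no action for Grade 3-4.
- **Section 8.2.7.1** refers hypersensitivity reactions to Appendix 6 and itself describes interruption and a 50% rate only for Grade 1 or 2.
- **Appendix 6 (Section 10.6)**. Grade 1-2: "Interrupt tusamitamab ravtansine infusion. Tusamitamab ravtansine may be resumed only after patient recovery, at half the previous infusion rate". Grade 3-4: interrupt, then "definitively discontinue tusamitamab ravtansine and consider infusion delay". The ramucirumab cell of the Grade 3-4 row reads "Interrupt ramucirumab infusion and definitively discontinue ramucirumab" and has no clause on delay.

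On which text governs, Section 8.2.7 says: "Management of AEs related to tusamitamab ravtansine and ramucirumab is summarized in Appendix 6". Section 6.5 likewise directs cycle delays and dose modifications to that appendix. Section 6.5 also says that if one of the two drugs "is prematurely permanently discontinued, the other drug can be continued until disease progression".

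**The concern.** Table 2 sets a lower grade for its rule but no upper one, and it attaches permission to resume to the whole open-ended range. A site that relied on this row could restart the infusion at half rate after a severe reaction, once the patient had recovered. Appendix 6 rules that out, giving symptomatic bronchospasm, hypotension and angioedema among its Grade 3-4 examples. What is at stake is rechallenge after a severe hypersensitivity reaction, so this is a matter of participant safety and not of estimation.

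The row cannot be set aside as pure background. Section 2.3.1 introduces the table as the mitigation to be used in this study, and the row's title brings anaphylaxis within its scope.

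**Working it through.** The documents give no figure to reproduce on this point. The main check is a comparison of texts, followed by the scale of the underlying event.

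**1. Instruction by grade**

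| IRR grade | Table 2 | Section 6.1 | Appendix 6 | Result |
|---|---|---|---|---|
| 1 | Flow rate may be lowered; interruption not mentioned | Must interrupt; resume at half rate after recovery | Interrupt; resume at half rate after recovery | Table 2 is incomplete |
| 2 | Interrupt; may resume at half rate after recovery | As for Grade 1 | As for Grade 1 | Agree |
| 3-4 | Interrupt; may resume at half rate after recovery | No instruction | Interrupt and stop permanently | Contradiction |

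Only the Grade 3-4 line contains two instructions that cannot both be followed. Appendix 6 is the only text that states the stop at that grade.

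**2. Which text prevails**

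Sections 6.5, 8.2.7 and 8.2.7.1 all point to Appendix 6, so it is the rule to keep. No sentence says that it overrides Table 2. The rule in Section 6.5 that the most conservative adjustment applies concerns a participant with several adverse events and conflicting recommendations. It does not address two protocol texts on one event.

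**3. Scale of the underlying event**

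Table 2 reports 1 patient with Grade 3 hypersensitivity (0.6%) and 1 with a Grade 1 IRR in pooled TED13751 data. That row prints no denominator. Assumption: it is the 160 patients at 100 mg/m² Q2W named in the keratopathy row.

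- Rate: 1/160 = 0.00625, or 0.63%, which agrees with the printed 0.6%.
- Exact 95% interval: the lower limit is 1 − 0.975^(1/160) = 0.016%; the upper limit, from P(X ≤ 1 | 160, p) = 0.025, is 3.43%.
- Expected in about 38 treated participants: 38 × 0.00625 = 0.24 (38 × 0.000158 = 0.006 to 38 × 0.03433 = 1.30).
- Chance of at least one: 1 − (1 − 0.00625)^38 = 21%, and about 73% at the upper limit, 1 − (1 − 0.03433)^38.

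These figures describe Grade 3 hypersensitivity, not wrong resumptions. The expected number of wrong resumptions would be 38 × p × f, where f is the share of such events that occur during an infusion and are handled from Table 2. The documents give nothing on f, which can lie anywhere from 0 to 1, so the product is not informative. In addition, p comes from monotherapy without ramucirumab and below the 170 mg/m² loading dose, and the Grade 3 case is not stated to have arisen during an infusion.

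**4. The extra clause in Appendix 6**

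A drug that has been stopped permanently has no later infusion to delay, so the closing clause of the Grade 3-4 tusamitamab ravtansine cell has no clear object. It may have been meant for ramucirumab, which can continue alone, but the cell does not say so. The retreatment criteria in Section 6.5.1 already hold further dosing until IMP-related toxicity is Grade 1 or lower, or back to baseline severity.

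**The case against.** The strongest reply is that Table 2 is a risk summary in the introduction. It labels this text as recommended and says only that the infusion may be resumed. The sections that sites work from are consistent with one another: Section 6.1 confines half-rate resumption to Grade 1-2, and three sections lead to Appendix 6. Section 6.5 also lets the investigator stop treatment for any adverse event that warrants it. All of this stands and keeps the practical risk small. It does not remove the contradiction, because one text permits what the other forbids and neither is declared subordinate.

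A reader might also infer four stronger points, which the documents do not support.

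- *That Table 2 contradicts the other sections at Grade 1.* It does not forbid interruption at Grade 1; it leaves it out. Lowering the flow rate is compatible with interrupting and then resuming at half rate. This is a minor misalignment.
- *That the clause on delay leaves ramucirumab timing open after a severe tusamitamab ravtansine reaction.* Section 6.5.1 largely answers this. Ramucirumab is also given first, so that cycle's ramucirumab infusion is already over.
- *That the missing stop is out of character for Table 2, because its neuropathy row states one at Grade 3-4.* The keratopathy, cardiotoxicity and hepatotoxicity rows also omit stops that Appendix 6 or Section 8.2.7.5 requires. The fault here is the permission to resume, not the omission alone.
- *That the 0.6% can be turned into an expected number of wrongly resumed infusions, or into an upper bound on them.* The share handled from Table 2 has no source. The 21% uses only the point estimate, and the figure is about 73% at the upper confidence limit.

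**Conclusion.** The point holds for Grade 3-4. As written, Table 2 permits half-rate resumption of tusamitamab ravtansine after a severe infusion reaction, against Appendix 6 and beyond what Section 6.1 provides. It is a stated safety instruction that would be wrong if followed, so it should be corrected even though sites are directed to the right rule elsewhere.

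Its size can be described only loosely: one Grade 3 hypersensitivity in the pooled earlier data, and no supportable estimate of how often Table 2 would be followed in its place. The conclusion rests on a literal reading of Table 2 and on Appendix 6 being the intended rule, which the cross-references support. It does not depend on the assumed denominator of 160. The Grade 1 wording and the clause on delay are secondary. Sample size, the ORR analysis and the other planned analyses are untouched.

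**What to change.** 1. In the hypersensitivity row of Table 2, restrict interruption and half-rate resumption to Grade 1-2. State permanent discontinuation of tusamitamab ravtansine at Grade 3-4, with a reference to Appendix 6. Starting interruption at Grade 1 also brings the row into line with Section 6.1 and Appendix 6.
2. As a minor copy-edit, delete the closing clause on infusion delay from the Appendix 6 Grade 3-4 tusamitamab ravtansine cell. If it was meant for ramucirumab, move it to that column and say so.

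The cost is two wording changes in a protocol clarification, with no new data and no change to the SAP.
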